5.1.3.1 Primary Effectiveness Endpoint

The primary effectiveness endpoint will be met if the responder rate at month 6 for the treatment group is statistically greater than that for the control group at month 6 and the observed responder rate at month 6 for the treatment group is greater than 50%. A responder is a subject who shows clinically significant improvement, i.e., ≥ 1 -point decrease, on the ACRS from baseline based on EI assessment of 2D renderings of the chin profile.

The primary effectiveness analysis is summarized in Table 5-15.

Table 5-15 Primary Effectiveness Analyses

Endpoint	Description	Timing	Methodology
Primary: Responder analysis based on photo ACRS	
• Superiority of the treatment group over no-treatment control group• Responder rate of treatment group is greater than 50%	Month 6	Responder

The primary effectiveness analysis will be performed on the mITT population without any missing data imputation. Sensitivity analysis will be performed using ITT and PP populations as well as using missing data handling conventions as described in Section 5.1.1.1.4. Additionally, sensitivity analysis will be performed on mITT subjects with a baseline ACRS photo score of 2 or 3.

5.1.3.2 Secondary Effectiveness Endpoint

[figure not shown]
The secondary effectiveness analysis is summarized in Table 5-16.

Table 5-16 Secondary Effectiveness Analyses

Endpoint	Description	Timing	Methodology
Secondary 1: Responder analysis based on GAIS (by EI and by subject)	Summary for treatment group	Month 6	Categorical
Secondary 2: Satisfaction with Chin module using overall score	Comparison of baseline vs. postbaseline for treatment group using 2-sided paired t-test	Month 6	CFB Paired T

A responder on GAIS is a subject who shows improvement in the overall aesthetic assessment in the chin area (corresponds to a response of “Improved” or “Much Improved” on GAIS).

The secondary effectiveness analysis for Satisfaction with Chin module of the FACE-Q questionnaire will be conducted only if the primary endpoint is met. No additional multiplicity adjustment or gatekeeping multiple comparisons procedures are needed.

5.1.4 Safety Analyses

Safety analyses will be based on the Safety Population.

5.1.4.1 Study Treatment Exposure and Compliance

See section 5.1.1.2.8.

5.1.4.2 Adverse Events

The following adverse event (AE) terms are defined:

Table 5-18 AE Terms

Term	Description
Treatment-emergent	Treatment group: An event that initially occurs or increases in severity on or after the treatment start date.
Adverse Event (TEAE)	Control group: An event that initially occurs or increases in severity on or after randomization date.

AEs and encompassing abnormalities, reported as occurring after the Screening Visit, will be coded using MedDRA version 18.1 or newer. A listing for all TEAEs in the treatment and control groups will be presented. Additionally, unique subjects reporting AEs as well as the number of events in the following AE categories will be summarized for treatment subjects, control subjects after optional treatment, and all treated subjects as follows:

Table 5-3 AE Summaries

Endpoint	Description	Timing	Methodology
Overall summary	Overall summary only for the following categories: 
 • Treatment-emergent AEs (TEAEs) • Treatment-related TEAEs • Treatment-related TEAEs at injection site • Treatment-related TEAEs not at injection site • All Serious AEs (SAE) • Treatment-related SAE • Discontinued due to TEAE • Deaths 	Treatment period	Categorical counts, Event descriptives
TEAEs	
 • Overall summary and by SOC, PT and severity 	Treatment period	Categorical counts, Event descriptives
Treatment-related TEAEs	
 • Overall summary and by SOC, PT and severity • Overall summary by severity, duration, time to onset, resolution, and treatment required 	Treatment period	Categorical counts, Event descriptives
SAEs	Overall summary and by PT	Treatment Period	Listing
AEs leading to discontinuation	Overall summary and by PT	Treatment Period	Listing

[figure not shown]
Note: SOCs will be sorted alphabetically; PTs will be sorted in descending frequency in the treatment group. AEs for control group before and after optional treatment are summarized separately.

[figure not shown]
Time to onset for TEAEs will be computed as

AE start date - reference date + 1,

where, the reference date is initial treatment date for TEAEs occurring on or after initial treatment but before touch-up treatment and the reference date is touch-up treatment date for TEAEs occurring on or after touch-up treatment but before repeat treatment.

Duration for TEAEs will be computed as AE end date – AE start date + 1.

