Appropriate injection volume for the chin and chin area will be determined by the Treating Investigator but is not to exceed a maximum total volume of 4.0 mL for initial and touch-up treatments combined, and 4.0 mL for repeat treatment.

DURATION OF STUDY: Treatment Group: Initial treatment period: up to 30 days; Follow-up period: 12 months following last treatment (initial or touch-up), and 1 month following optional repeat treatment. Control Group: Control period: 6 months; Initial treatment period: up to 30 days; Follow-up period: 6 months following last treatment (initial or touch-up)

RESPONSE MEASURES:

Effectiveness: The primary effectiveness measure is the EI's photo assessment of chin retrusion using the ACRS at month 6 based on 2D profile images of the left side of the chin rendered by the Canfield image analysis technician from the 3D images. Secondary effectiveness measures include EI and subject assessments of global aesthetic improvement in the chin area using the 5-point GAIS, and subject responses on the Satisfaction with Chin module of the validated FACE-Q questionnaire.

STATISTICAL METHODS:

Sample Size Calculation: Sample size is determined to provide adequate power to demonstrate that the product is effective as well as safe. A sample size of 120 subjects in the treatment group and 40 subjects in the control group will provide > 99% power to detect a difference of at least 40% in the responder rates between the groups. This calculation is based on a 2-sided Fisher's exact test at the 5% level. The treatment group is assumed to have at least 80% responder rate and the control group will have at most 40% responder rate. Assuming a screen fail rate of 15% and a drop-out rate of 15% between randomization and the month 6 visit, up to 224 subjects will be enrolled, resulting in up to 168 subjects randomized to the treatment group and up to 56 subjects to the control group (3:1 ratio). Assuming a screen fail rate of 15% and an overall drop-out rate of 20% between randomization and study completion, an estimated 152 subjects will complete the study.

With up to 168 subjects randomized to the treatment group and an estimated screen fail rate of 15%, it is estimated that at least 143 subjects will be treated in the study. With 143 treated subjects, there is at least an 88% power to detect an AE related to treatment with an incidence rate of 1.5% in the population using a 1-sided exact binomial test at the 2.5% level.

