4.2 Duration

The study will span a total of approximately 23 months: an estimated 9 months for recruitment, 1 month for treatment, and up to 13 months for follow-up. Participation for each subject randomized to the treatment group will encompass up to 1 month for screening, up to 1 month for treatment, 12 months of follow-up after the last treatment (initial or touch-up), and 1 month of follow-up after optional repeat treatment. Participation for each subject in the control group will encompass up to 1 month for screening, 6 months for the no-treatment control period, up to 1 month for optional treatment, and 6 months of follow-up after the last treatment (initial or touch-up).

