5.1.1.3 Statistical Methodology

The methodologies defined below apply as specified to individual endpoints defined in this SAP.

Table 5-2 Statistical Methodology

Methodology	Description
Categorical counts	
 Number and percent of subjects in individual categories 
 Subjects with ≥ 1 qualifying event counted once per individual category N included = participants with non-missing value for by visit analysis
Event descriptives	
 Number and percentage of events in individual categories 
 Events counted individually for each instance Percentage denominator = total number of events
Continuous descriptives	
 N included, mean, standard deviation (SD), median, minimum, maximum N included = subjects with non-missing value
CFB descriptives	
 Continuous descriptives for baseline, postbaseline, and change from baseline (CFB) values N included = subjects with non-missing values at both baseline and the specified postbaseline analysis visit
CFB Paired T	
 Continuous descriptives for baseline, postbaseline, and CFB values 
 P-values from a 2-sided paired t-test comparing baseline and postbaseline values N included = subjects with non-missing values at both baseline and the specified postbaseline analysis visit
Responder	
 Categorical descriptives for responders and nonresponders 
 Include count and percent along with exact binomial 95% CI P-values from 2-sided Fisher's exact test N included = with non-missing values at both baseline and the specified postbaseline analysis visit

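### The pooled all-treated adverse event column mixes up to 13–14 months of follow-up with up to 7, so late events are diluted there

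*SAP*

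**What the plan says.** SAP 5.1.4.2 states that subjects with AEs, and the number of events, "will be summarized for treatment subjects, control subjects after optional treatment, and all treated subjects as follows". The note under the AE summaries table adds: "AEs for control group before and after optional treatment are summarized separately". The methods named are categorical counts and event descriptives. SAP 5.1.1.3 defines the first as "Number and percent of subjects in individual categories", with each subject counted once per category, and the second as a share of all events. Neither uses time at risk.

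The definition of a treatment-emergent AE (TEAE) fixes a start but no end. For the treatment group it starts at treatment. For controls it reads: "Control group: An event that initially occurs or increases in severity on or after randomization date". Protocol 11.2 collects AEs to the last subject visit, and SAP 6.2.2 says TEAEs need no analysis visit windows. Each column's risk period is therefore however long its subjects stay in the study.

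Those periods differ by design. Protocol 4.2 gives the treatment group "12 months of follow-up after the last treatment (initial or touch-up), and 1 month of follow-up after optional repeat treatment", after a treatment window that the synopsis describes as "Treatment Group: Initial treatment period: up to 30 days". Controls have "6 months for the no-treatment control period, up to 1 month for optional treatment, and 6 months of follow-up after the last treatment".

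The AE summaries carry the timing label of treatment period, which the readable text does not define for AEs. The time-to-onset rule in SAP 5.1.4.2 stops at repeat treatment, whereas SAP Table 6-1 defines a separate Safety Day after it. Whether post-repeat events enter these columns is not stated.

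**The concern.** The all-treated column is the one most naturally read as the overall safety figure for the device. It divides events by everyone treated, although about a fifth of that denominator (40/183 under the assumption used below) is observed for roughly half as long as the rest. The result is not a risk over any defined time. For late-onset events it lies below what the longer-followed subjects show.

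Evaluating safety is a stated objective. The treatment group's first 6 months, set against the control period, is the only concurrent randomized safety information the design yields, and no readable AE table isolates it.

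**Working it through.** **The plan's own safety figure.** Protocol 8.5 gives 168 × 0.85 = 142.8, rounded to 143 treated, and at least 88% power for a 1.5% AE. The chance of at least one such event is 1 − (1 − 0.015)^143 = 88.5%, so the figure reproduces. It is not affected by this point, although the 1.5% carries no time frame.

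**Maximum follow-up from the start of each period (Protocol 4.2 and synopsis).**

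| Group | Sum | Months |
|---|---|---|
| Treatment group, no repeat | 1 + 12 | 13 |
| Treatment group, with repeat | 1 + 12 + 1 | 14 |
| Controls after optional treatment | 1 + 6 | 7 |
| Control period | 6 | 6 |

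These are maxima; 14 needs both the full touch-up window and the repeat treatment.

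**Dilution in the pooled column.** If an event can be seen only after treated controls have left, the pooled percentage divided by the treatment-group percentage is n_T/(n_T + n_C). Here n_T = 143. The number of controls who take optional treatment, n_C, is not in the documents and is assumed:

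- n_C = 24 (about half of the next line): 143/167 = 86%
- n_C = 40: 143/183 = 78%
- n_C = 48 (56 × 0.85 = 47.6): 143/191 = 75%

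The 3:1 allocation with every control treated gives the same floor, 3/4 = 75%. No hazard model is needed.

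**Events spread evenly over time.** Assume a constant hazard that gives 10% over 6 months. The incidence over t months is 1 − 0.90^(t/6): 11.6% at 7, 20.4% at 13 and 21.8% at 14. The pooled value is (143 × 21.8% + 40 × 11.6%)/183 = 19.6%, about 90% of the treatment-group value.

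**Early events.** If all events follow soon after injection and nobody has repeat treatment, the treated columns agree and the ratio is 1.0. Repeat treatment changes that if post-repeat events are counted. At an assumed 20% per course and repeat uptake u, the treatment-group figure is 1 − 0.80 × (1 − 0.20u): 28% at u = 0.5 and 36% at u = 1, against 20% in treated controls.

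**Mixed course.** With acute risk q and a background of r per 6 months, incidence is 1 − (1 − q)(1 − r)^(t/6). The 14-to-7-month ratio is 28.5%/26.7% = 1.06 for q = 25%, r = 2%, and 29.6%/20.4% = 1.45 for q = 10%, r = 10%.

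**A reader's comparison with the control period.** Under a constant, identical hazard, the 14-to-6-month ratio of percentages runs from 2.32 (1% at 6 months) to 1.88 (30% at 6 months) with no device effect. At 10% it is 21.8/10.0 = 2.18. For events confined to the first weeks, the longer window adds nothing.

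**The case against.** **No treated-versus-control contrast is planned.** A reader might infer that the SAP compares AE rates over 13–14 months with rates over 6, so that a harmless device would look harmful. The documents do not support that. All three groups listed in SAP 5.1.4.2 are treated groups, control-period AEs are summarized apart from them, and no difference or test is specified. SAP Table 4-1 sets out to compare effectiveness with control, but only to evaluate safety. This objection stands. What remains is that a control-period summary will exist and can be set beside the treatment column.

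**Late events are not hidden.** The treatment-group column shows them at their full crude rate, treatment-related TEAEs are summarized by time to onset, and all TEAEs are listed. This also stands; the dilution is confined to the pooled column.

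**The size depends on an unknown time course.** In the cheek study described in Protocol 2.2, 99% of AEs were at a treatment site, and a similar profile is expected in the chin. That makes a pure background-hazard model a poor description of most AEs. But site is not timing, and the documents give no onset distribution for AEs, so a range is the honest statement.

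**Redaction.** List entries between SAP Tables 5-19 and 5-26 are blacked out, the SAP design summary is unreadable, and the text passes from 5.1.4.2 to 5.1.6. A by-period safety table or a definition of the treatment period could be there. The readable statement that TEAEs need no visit windows makes this less likely but does not exclude it.

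**Conclusion.** The point holds for the pooled column. As written, it gives a crude percentage over unequal follow-up (up to 13 or 14 months against up to 7) and understates events that arise only after treated controls have left. They show at about 78% of the treatment-group rate with 143 and an assumed 40 subjects, and at 75% to 86% over the range tried. Evenly spread events show at about 90% under the constant-hazard assumption with all treatment-group subjects followed for 14 months. Early injection-related events are essentially unaffected unless post-repeat events are counted.

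For the control period, the supportable statement is narrower: a reader who sets the separate summaries side by side compares 6 months with up to 13–14. The resulting inflation is anywhere from nil to about 2.3-fold, depending on assumptions about timing that the documents do not settle. It would be wrong to treat the upper end, or 14 months of follow-up, as the expected case.

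No stated figure is wrong and no planned test changes. This is a worthwhile, inexpensive improvement to descriptive safety tables.

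**What to change.** In SAP 5.1.4.2:

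- (a) Base the all-treated summary of TEAEs and serious AEs on a window common to both treated groups: first injection to month 6 after last treatment.
- (b) Show treatment-group events after month 6, and events after repeat treatment, in separate columns. The denominator of each should be the subjects actually followed in that period.
- (c) For the randomized comparison with the control period, use equal lengths: the first 6 months from initial treatment against the first 6 months from randomization. A cut at the month 6 visit after last treatment would not do, because it sets up to 7 months against 6.
- (d) State whether the treatment period includes events after repeat treatment.

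The cost is SAP wording and a few extra tables from data already collected, with no change to conduct. SAP Table 5-5 already cuts disposition at month 6. If the redacted tables already contain a by-period summary, only the missing parts need adding.

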4.3.4 Retreatment Criteria

The subject may undergo a touch-up treatment 30 days after the initial treatment (ie, at the month 1 follow-up visit) if both the subject and TI determine that optimal correction has not been achieved and total treatment has been less than 4.0 mL. The total injection volume for an individual subject for the initial and touch-up treatments combined cannot exceed 4.0 mL.

Subjects in the treatment group may undergo repeat treatment 12 months after the last treatment (ie, at the month 12 follow-up visit after all procedures are completed). The total injection volume for repeat treatment cannot exceed 4.0 mL.

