5.1.2.8 Exposure to Study Treatment

Treatment exposure related variable will be summarized for safety population by treatment group as follows:

Table 5-11 **Exposure to Study Treatment**

Endpoint	Description	Timing	Methodology
Volume injected	Initial, Touch-up, Combined initial and touch-up, Repeat	Treatment period	Continuous descriptives

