6.1 Analysis Days

Treatment Day for effectiveness, [REDACTED] and AE are defined as follows:

Table 6-1 Analysis Day Definitions

Term	Description
Effectiveness [REDACTED] Effectiveness Day	Treatment Group and Control Group (only the control subjects receiving optional treatment): Relative to the last treatment date (either the initial treatment, if no touch-up is performed, or the touch-up treatment) 
○ Effectiveness Day = analysis date – last treatment start date + 1○ Effectiveness Day 1 = last treatment start date Control (before receiving optional treatment): Relative to the randomization date 
○ Effectiveness Day = analysis date – randomization date +1○ Effectiveness Day 1 = randomization date
Safety (including AE [REDACTED] Safety Day)	Treatment Group and Treated Control (i.e., only the control subjects receiving optional treatment): Relative to treatment date (initial and touch-up) Safety Day = analysis date – initial treatment date + 1 Safety Day 1 = initial treatment date Control (before receiving optional treatment): Relative to the randomization date 
○ Safety Day = analysis date – randomization date +1○ Safety Day 1 = randomization date Treatment Group Only: Relative to the repeat treatment date (after repeat treatment) Safety Day = analysis date – repeat treatment date + 1 Safety Day 1 = repeat treatment date

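### The time-to-onset rule for adverse events gives no reference date after repeat treatment, so onset there is counted from about a year earlier or left undefined

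*SAP*

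**What the plan says.** SAP 5.1.4.2 computes time to onset as "AE start date - reference date + 1" and then defines the reference date for two intervals. For the first, "the reference date is initial treatment date for TEAEs occurring on or after initial treatment but before touch-up treatment". For the second, "the reference date is touch-up treatment date for TEAEs occurring on or after touch-up treatment but before repeat treatment". The rule stops there. Repeat treatment closes the second interval, but no third interval opens.

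Events after repeat treatment are nevertheless in scope:

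- Protocol 4.3.4 allows the repeat injection: "Subjects in the treatment group may undergo repeat treatment 12 months after the last treatment".
- Protocol 4.2 provides one month of follow-up after it, and Protocol 11.2 collects adverse events until the last visit.
- The treatment-group TEAE definition in SAP 5.1.4.2 has a start but no end: "An event that initially occurs or increases in severity on or after the treatment start date".
- For treatment-related TEAEs, the AE summary table in SAP 5.1.4.2 asks for "Overall summary by severity, duration, time to onset, resolution, and treatment required", with the treatment period as its timing. SAP 5.1.2.8 uses the same period for volume injected at "Initial, Touch-up, Combined initial and touch-up, Repeat".

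Table 6-1 in SAP 6.1 defines a separate variable, Safety Day. It does have a clause for this situation, headed "Treatment Group Only: Relative to the repeat treatment date (after repeat treatment"), in which Day 1 is the repeat treatment date.

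**The concern.** Time to onset should tell a reader how long after an injection an event began. After repeat treatment, the printed rule either measures from an injection about a year earlier or gives nothing. Which of these happens depends only on whether the subject had an optional touch-up in the first course, and that has no bearing on the repeat injection.

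In the time-to-onset breakdown, a reaction that began within days of the repeat injection could therefore sit beside events that truly began a year after treatment, or be missing. Two programmers working from the same text could also produce different tables. The columns exposed are those for the treatment group and for all treated subjects. Control subjects have no repeat treatment in the plan.

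**Working it through.** The plan gives no figure to reproduce, so the check applies the printed rule to example subjects and compares the result with Safety Day.

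**Inputs**

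- Onset formula and the two reference intervals: SAP 5.1.4.2.
- Safety Day after repeat treatment = analysis date − repeat date + 1: SAP Table 6-1.
- Touch-up optional, 30 days after initial treatment: Protocol 4.3.4.
- Repeat treatment 12 months after the last treatment (Protocol 4.3.4) or 12 months after initial treatment (Protocol 9.1.3). Both were tried.
- Follow-up after repeat treatment of one month: Protocol 4.2.
- Assumptions: initial injection on day 0, 12 months = 365 days, and an event starting *k* = 0, 3, 14 or 30 days after repeat treatment.

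**Subject without a touch-up.** Repeat treatment falls on day 365 under either protocol section, because the initial treatment is also the last. No touch-up date ever ends the first interval, so the reference date stays at day 0:

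- onset = (365 + *k*) − 0 + 1 = 366 + *k*
- Safety Day = (365 + *k*) − 365 + 1 = 1 + *k*

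**Subject with a touch-up on day 30.** Repeat treatment falls on day 30 + 365 = 395 (Protocol 4.3.4) or day 365 (Protocol 9.1.3). The event is after touch-up, so the first interval does not apply. It is not before repeat treatment, so the second does not apply either. Onset is undefined. If a programmer carried the touch-up date forward, which the text does not say to do, onset would be (395 + *k*) − 30 + 1 = 366 + *k*, or (365 + *k*) − 30 + 1 = 336 + *k*.

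| Days after repeat (*k*) | Rule, no touch-up | Rule, touch-up | Touch-up date carried forward | Safety Day |
|---|---|---|---|---|
| 0 | 366 | undefined | 366 or 336 | 1 |
| 3 | 369 | undefined | 369 or 339 | 4 |
| 14 | 380 | undefined | 380 or 350 | 15 |
| 30 | 396 | undefined | 396 or 366 | 31 |

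Without a touch-up, the rule exceeds Safety Day by (366 + *k*) − (1 + *k*) = 365 days at every *k*.

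**Is a difference from Safety Day an error in itself?** No. Take an event 3 days after a touch-up on day 30. Table 6-1 still counts from initial treatment, so Safety Day is 33 − 0 + 1 = 34. Time to onset restarts at touch-up and is 33 − 30 + 1 = 4. The two variables differ there because they are defined differently. After repeat treatment the position is not the same: Table 6-1 restarts its clock, while the onset rule, otherwise the finer of the two, has no clause at all. That looks like an omission.

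**The case against.** The strongest reply is that day 366 is only one reading. It keeps the interval before touch-up open indefinitely for a subject who never has one. The rule could instead be read as covering the first course only, which would leave events after repeat treatment unaddressed for everyone. That is a fair reading, and on it the 365-day excess does not arise. The gap remains, however, and now covers all repeat-treated subjects. A stricter reading, in which the first interval needs an actual touch-up date, would leave even a first-week event without an onset value in any subject who had no touch-up. No reading yields a usable value after repeat treatment.

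A reader might also infer more than the documents support:

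- *That the onset rule contradicts Table 6-1 throughout.* The two give conflicting day counts only for subjects without a touch-up, on the literal reading. For subjects with a touch-up there is a missing value, not a conflict.
- *That these events drop out of the safety report.* They remain in the overall counts, in the tables by system organ class, preferred term and severity, and in the TEAE listing.
- *That the table would lead to a wrong safety conclusion, because late onset is a recognised signal for fillers.* Neither document says so, and the output is descriptive with no test attached.

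The number of events is also uncertain. Protocol 8.4 refers to injection site responses collected in 30-day diaries, and the visible text does not show when such a response becomes an adverse event. Parts of the SAP's safety section are redacted, and a separate summary for repeat treatment may exist there. It would not complete the legible rule for the summary that the rule governs.

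**Conclusion.** The point holds as a defect in a derivation rule, with limited reach. For events 0 to 30 days after repeat treatment, SAP 5.1.4.2 read literally gives about day 366 to 396 for subjects without a touch-up and no value for those with one. Safety Day for the same events is 1 to 31.

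The figures assume a 365-day year, repeat treatment at exactly 12 months and, for the second group, a touch-up on day 30. Actual visit dates would shift them slightly without changing the pattern. The share of the summary affected cannot be calculated, because the documents give neither the number of repeat-treated subjects nor the number of treatment-related events after repeat treatment. The primary effectiveness analysis is untouched. The rule should still be corrected, since following it as printed produces misleading or missing onset values.

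**What to change.** In SAP 5.1.4.2, define the reference date as the most recent study treatment on or before the event's start date:

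- the initial treatment date, until touch-up or repeat treatment, whichever comes first;
- the touch-up date, until repeat treatment;
- the repeat treatment date, for events on or after repeat treatment.

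The first line also settles the case of a subject with no touch-up. Events 0, 3, 14 and 30 days after repeat treatment then have onsets of 1, 4, 15 and 31 days. After repeat treatment this agrees with Safety Day in Table 6-1. Between touch-up and repeat treatment the two variables will still differ by design, so the SAP should not describe them as identical.

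The cost is one sentence and a small programming change before database lock. No new data are needed, since Table 6-1 already relies on the repeat treatment date. Separately, Protocol 4.3.4 and 9.1.3 count the 12 months to repeat treatment from different dates for subjects with a touch-up and should be reconciled. The onset rule above works under either.
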